**4. Study Population:**

**A. A target of at least 200 pediatric patients who received an allogeneic HSCT over three enrollment years (2016-2017, 2017-2018, 2018-2019) and met the inclusion/exclusion criteria outlined below:**

**1. Inclusion criteria**

- a. Allogeneic HSCT recipients who are 3-35 months post-transplant;
- b. 3-17 years of age, inclusive;
- c. Available for duration of study;
- d. Patients with stable GVHD for at least 4 weeks will be eligible (stable is defined as having no major increases in systemic immunosuppressive therapy for GVHD; adjustments of established medications to obtain a stable target level are acceptable and do not impact eligibility). Parent/legal guardian willing and capable of signing written informed consent;
- e. Parent/legal guardian expected to be available for entire study;
- f. Parent/legal guardian can be reached by telephone and/or electronic communication.
- g. Subjects must have a platelet count of  $\geq 30,000$  to receive the immunizations. Patients requiring platelet transfusions are eligible to enroll and must have a platelet count  $\geq 30,000$  within 72 hours prior to their immunization, or platelet count  $\geq 75,000$  without transfusion documented within 30 days for subjects <12 months post-transplant and within 90 days for subjects 12-35 months post-transplant.

**2. Exclusion criteria**

- a. History of hypersensitivity to previous influenza vaccination or severe hypersensitivity to eggs/egg protein;
- b. History of Guillain-Barre syndrome;
- c. Evidence of hematologic malignancy or disease relapse post-transplant (stable mixed chimerism is permitted);
- d. History of receiving current year seasonal influenza vaccine post-transplant;
- e. Pregnant female;
- f. History of proven influenza disease after September 1, 2018 prior to enrollment
- g. Non-allogeneic (e.g. autologous) or syngeneic hematopoietic SCT recipients;
- h. History of known active infection with HIV, Hepatitis B or Hepatitis C;
- i. History of known severe latex hypersensitivity;
- j. Subjects who have received stem cell boost or delayed donor lymphocyte infusion within 90 days prior to enrollment, including day of enrollment;
- k. Receipt of IVIG/SCIG <27 days prior to calendar day of vaccination;
- l. Subjects who have participated in year 1 and/or 2 of the study, and received study vaccine

**Criteria for temporarily delaying vaccine administration:** The following conditions are temporary or self-limiting, and a subject may be included in the study once the condition has resolved, provided that the subject is otherwise eligible: 1). Fever  $\geq 100.4^{\circ}\text{F}/38.0^{\circ}\text{C}$  (oral measurement), or an acute illness within 48 hours of

# Comparison of High vs. Standard Dose Flu Vaccine in Pediatric Stem Cell Transplant Recipients

DMID Protocol Number 16-0117

Protocol Version 8.0

Date: 9/12/2019

enrollment 2). Receipt of any live vaccines within four weeks or any inactivated vaccines within two weeks prior to potential study vaccination.

Note: if patients were eligible for vaccine 1, they will be eligible to receive vaccine 2 regardless of any changes on their GVHD status, unless it is deemed not medically safe to receive influenza vaccine.

For subjects who were enrolled and vaccinated in 2016-17, 2017-18, or 2018-19, the goal is to enroll individuals who participated in the previous influenza season year and administer the same vaccination as the previous year. These subjects are referred to as repeaters. For example, subjects enrolled in 2016-17 could re-enroll in 2017-18, subjects enrolled in 2017-18 could re-enroll in 2018-19, and subjects in 2018-19 are deemed eligible to re-enroll in 2019-20 as repeaters. Subjects may only enroll as a repeater one time and must enroll the year after their original enrollment. Subjects must receive at least one vaccine to be eligible as a repeater in the subsequent year.

## **B. Enrollment Criteria for Subjects who Participated in the previous influenza season**

- Repeaters will retain their original study ID and their randomization number
- Previous screen failures will not be enrolled.
- If visit 4 from the previous influenza season and visit 1 from the current influenza season year occur on the same day, lab results from visit 4 (prior to consent) can be part of visit 1.

### **1. Inclusion criteria**

- a. Available for duration of study;
- b. Patients with stable GVHD for at least 4 weeks will be eligible (stable is defined as no major change in systemic immunosuppressive therapy for worsening GVHD; adjustment of actual dose to obtain a stable target level is acceptable).
- c. Subjects must have a platelet count of  $\geq 30,000$  to receive the immunizations. Patients requiring platelet transfusions are eligible to enroll and must have a platelet count  $\geq 30,000$  within 72 hours prior to their immunization, or platelet count  $\geq 75,000$  without transfusion documented within 30 days for subjects <12 months post-transplant and within 90 days for subjects 12-35 months post-transplant.
- d. Parent/legal guardian willing and capable of signing written informed consent;
- e. Parent/legal guardian expected to be available for entire study;
- f. Parent/legal guardian can be reached by telephone and/or electronic communication.

### **2. Exclusion criteria**

- a. History of hypersensitivity to previous influenza vaccination or severe hypersensitivity to eggs/egg protein;
- b. History of Guillain-Barre syndrome;
- c. Evidence of hematologic malignancy or disease relapse post-transplant (stable mixed chimerism is permitted);
- d. History of receiving current year seasonal influenza vaccine post-transplant;
- e. Pregnant female;
- f. History of proven influenza disease after September 1, 2019 but prior to enrollment
- g. History of known active infection with HIV, Hepatitis B or Hepatitis C;
  - h. Subjects who have received stem cell boost or delayed donor lymphocyte infusion within 90 days of enrollment, including day of enrollment
  - i. Receipt of IVIG/SCIG <27 days prior to calendar day of vaccination
  - j. Non-allogeneic (e.g. autologous) or syngeneic hematopoietic SCT recipients;
  - k. Subjects who have participated in year 1 and/or 2 of the study and received study vaccine.

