**8. Study Withdrawal / Discontinuation:**

**a. Reasons for Withdrawal or Discontinuation of Study Product**

- 1. Subjects will be able to withdraw from the study at any time point.
- 2. A study subject will be discontinued from participation in the study if the following occur:

- a. Any clinical adverse event (AE), laboratory abnormality, intercurrent illness, or other medical condition or situation occurs such that continued participation in the study would not be in the best interest of the subject. However, the subject may continue to be followed for safety purposes.
- b. Development of any exclusion criteria may be cause for discontinuation from the study, except for individuals who were 17 at enrollment and turned 18 year old during the study.
- c. Subjects may be removed from the study for failure to make follow-up visits.
- d. Subjects may be removed from the study if new information becomes available that makes further participation unsafe.

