**d. Dosage, Preparation and Administration of Study Intervention/ Investigational Product**

Either dose (0.5 ml) of TIV or QIV (Fluzone® HD-TIV, Sanofi Pasteur) or (Fluzone Quadrivalent®, Sanofi Pasteur) will be administered intramuscularly in either the right or left arm. In preparing either vaccine, the pre-filled syringe will be gently shaken and visually inspected for particulate matter and/or discoloration prior to administration (the TIV/QIV may normally be clear to slightly opalescent). If either condition exists, the pre-filled syringe will not be used.

Subjects will be randomized in a 1:1 fashion to receive either 2 doses of 0.5 mL HD-TIV (60µg of each influenza antigen) or 2 doses of standard dose QIV (15µg of each influenza antigen) of the current seasonal influenza vaccine (e.g. 2016-2017 or 2017-2018 or 2018/2019 or 2019/2020) 28-42 days apart. The repeaters retain their randomization code.

Each of these study products will be labeled according to manufacturer specifications and include the statement "Caution: New Drug – Limited by Federal Law to Investigational Use."

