only a limited quantity of egg protein, this protein can induce immediate hypersensitivity reactions among persons who have severe egg allergy. Persons who have experienced hives, have had swelling of the lips or tongue, or have experienced acute respiratory distress or collapse after eating eggs should consult a physician for appropriate evaluation to help determine if vaccine should be administered. Persons who have documented immunoglobulin E (IgE)-mediated hypersensitivity to eggs, including those who have had allergic responses to egg protein—also might be at increased risk for allergic reactions to influenza vaccine, persons with known allergies to eggs or who developed an allergic reaction to previous influenza vaccines will not be enrolled in this study. The tip caps of the prefilled syringes may contain natural rubber latex, which may cause allergic reactions in latex sensitive individuals. (Therefore, individuals with history of hypersensitivity to previous influenza vaccination or severe hypersensitivity to eggs/egg protein are excluded).

The adverse event profile of TIV administration in pediatric immunocompromised recipients has been comparable to that reported in healthy individuals receiving TIV. With the exception of soreness at the injection site, adverse reactions to TIV are uncommon. Minor reported side effects include: low grade fever, chills, local redness, bruising, pain, swelling at injection site, headache, malaise, and/or joint or muscle pain. Very rare side effects include severe weakness or unusual feeling in the arms or legs, high fever, and/or unusual bleeding. In some years, Guillain-Barre syndrome has been reported but rarely in children.

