## 13. Study Visit Schedule: (see Table 3 for details)

- a. **Screening:** Subjects will be screened by history and physical exam to make sure that all eligibility criteria are met. No baseline laboratory screening will be performed prior to enrollment. However, if CBC d/p, quantitative CD4, CD8, CD19, IgM and IgG are obtained as part of standard of care prior to enrollment and on the same calendar day as vaccination, these data will be collected and will not need to be repeated after consent is signed. In addition, consent may be obtained prior to visit 1.
- b. **Enrollment/Baseline:** Prior to each vaccination, inclusion and exclusion criteria, as well as any reason to delay vaccination will be reviewed.
- c. **Follow up:** Follow-up telephone and/or electronic communication will be completed both 1-3 and 8-10 days after each vaccination visit. If the subject is seen as part of the optional visit and this visit is within

the 8-10 days communication window period, this would replace the 8-10 day telephone and/or electronic communication.

**d. Final Study Visit:** The final visit will be  $180 \pm 42$  days after visit 2.

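### The repeater exclusion list carries over 11 of the 12 first-entry exclusions and omits only severe latex hypersensitivity, although repeaters receive the same pre-filled-syringe products

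*Protocol*

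**What the plan says.** First-entry exclusions are in Protocol C.4.A.2. Item a covers reactions to influenza vaccine and egg, and item i is "History of known severe latex hypersensitivity".

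Repeater exclusions are in Protocol C.4.B.2. Item a is "History of hypersensitivity to previous influenza vaccination or severe hypersensitivity to eggs/egg protein", word for word as at first entry. Latex appears neither in that list nor in the repeater enrolment rules, the repeater inclusion criteria, or the reasons for delaying vaccination and the notes that follow.

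The exposure is described elsewhere:

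- Both products come in the same presentation (C.10.d): "In preparing either vaccine, the pre-filled syringe will be gently shaken and visually inspected for particulate matter and/or discoloration prior to administration".
- The side-effects section (C.11.b) warns: "The tip caps of the prefilled syringes may contain natural rubber latex, which may cause allergic reactions in latex sensitive individuals". The exclusion sentence that follows names only the other allergies: "individuals with history of hypersensitivity to previous influenza vaccination or severe hypersensitivity to eggs/egg protein are excluded".
- A repeater must have had at least one study vaccine and is given the same vaccine as the year before (C.4.A, repeater paragraph). SAP 1.1.3 confirms two doses of the same formulation.
- The lists are operative before both doses (C.13.b and Table 3): "Prior to each vaccination, inclusion and exclusion criteria, as well as any reason to delay vaccination will be reviewed".

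**The concern.** An exclusion tied to the syringe should apply whenever that syringe is used. The reason for item i does not change between a child's first and second season, because the product and presentation are the same. A site working from the repeater list would nevertheless find nothing about latex.

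What is at stake is safety. A severe reaction would harm a child. It could also interrupt the trial, since halting rule 5 (C.16.j) is met by one case of laryngospasm, bronchospasm or systemic anaphylaxis within 24 hours of vaccine. Remaining enrolment and vaccinations would then wait for DSMB review.

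**Working it through.** No figure in the plan bears on this point, so the check is a comparison of the two lists.

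**Step 1. Match the items (shortened here in my words).**

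| First entry (C.4.A.2) | Subject | Repeater (C.4.B.2) |
|---|---|---|
| a | influenza vaccine or egg allergy | a |
| b | Guillain-Barré syndrome | b |
| c | malignancy or relapse | c |
| d | this season's vaccine already given | d |
| e | pregnancy | e |
| f | proven influenza this season | f (date moved from 2018 to 2019) |
| g | autologous or syngeneic transplant | j |
| h | HIV, hepatitis B or C | g |
| **i** | **severe latex allergy** | **none** |
| j | recent cell boost or donor lymphocytes | h (slightly reworded) |
| k | recent immunoglobulin | i |
| l | took part in study year 1 or 2 | k |

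Result: 12 first-entry items, 11 matched in substance, 12 − 11 = 1 unmatched, which is latex.

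**Step 2. Does screening at first entry explain the omission?** If stable history items were dropped because they had already been checked, then egg allergy, Guillain-Barré syndrome and transplant type would be missing too. All three are asked again (repeater items a, b and j). The list was also adapted to the season, since repeater item f reads "History of proven influenza disease after September 1, 2019 but prior to enrollment". The documents give no reason for leaving out latex.

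**Step 3. Which children does the omission leave uncovered?**

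- Severe latex allergy known at first entry: barred then by item i, so the child never became eligible as a repeater.
- A reaction to an earlier study dose: arguably caught by repeater item a, as hypersensitivity to a previous influenza vaccination.
- Severe latex allergy first recognised between seasons by another route: not caught by any repeater item.

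Only the third group remains.

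**Step 4. What protects that child?**

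- C.8.a item 2a requires discontinuation when an "other medical condition or situation occurs such that continued participation in the study would not be in the best interest of the subject". It applies, but only if the investigator learns of the allergy and acts on it.
- C.8.a item 2b allows discontinuation when an exclusion criterion develops. It is permissive, and it is a matter of reading whether it reaches a criterion found only on the first-entry list.
- The note after the repeater criteria lets a second dose be withheld if influenza vaccination is judged medically unsafe. It does not cover the first dose of the repeat season.

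**Step 5. Size.** Each repeater is due 2 further injections. Under this protocol version the repeaters concerned are those of 2019-20, first enrolled in 2018-19 (C.1). Their number, the rate of newly recognised latex allergy and whether the 2019-20 tip caps contained latex are not in the documents, so no expected count can be calculated.

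**The case against.** The strongest reply is that other provisions already cover the case. Item 2b of C.8.a speaks of any exclusion criterion, and latex is one in this study. Repeaters keep their study ID and randomization number and are not re-randomized, so they can be seen as continuing participants to whom the first-entry list still applies. Sites also have the C.11.b warning, which covers both vaccines, and are to have the season's package inserts. Subjects are screened by history and examination, and past medical history is collected. The investigator is therefore not uninformed.

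Much of this stands, and it is why the point is minor. It does not remove the inconsistency. Item 2b is discretionary, and its reach is uncertain because the protocol gives repeaters their own list. The other provisions rely on the allergy coming up without a specific question, whereas an exclusion line makes the site ask before each dose.

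A reader might infer something stronger: that a child turned away for latex at first entry could now be vaccinated as a repeater. The documents do not support that. Both the protocol and SAP 1.1.3 require at least one study vaccine, which such a child would not have had. The closing note in C.4.B that lets unvaccinated screen failures enrol conflicts with the opening rules of C.4.B, but it does not turn such a child into a repeater.

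Nor do the documents show a deliberate decision to accept latex-allergic repeaters. The omission looks like a drafting slip.

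**Conclusion.** The point holds as a minor, low-probability safety inconsistency. The count is certain: 11 of 12 exclusions carried over, and one, severe latex hypersensitivity, left out. The practical gap is limited to a child eligible at first entry whose severe latex allergy is first recognised between seasons, other than through a study dose. It would be wrong to say that this child has no protection. What remains is investigator judgement rather than a listed criterion.

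Two assumptions matter: that the tip caps in use contain latex, which the protocol states only as a possibility, and that such a child exists among the 2019-20 repeaters. The likely number is zero or very few; that is a judgement, since the documents give no figures. The primary analysis is not affected. Repeater data have their own analyses (SAP 5.5 and 6.2), under a tertiary HAI objective and a secondary safety objective.

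**What to change.** Add first-entry item i, "History of known severe latex hypersensitivity", to the repeater list in C.4.B.2. The two lists would then agree on 12 of 12 items, and the eligibility review before each vaccination would cover latex for repeaters. For consistency, the exclusion sentence after the latex warning in C.11.b could name latex as well.

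The cost is one line in an amendment or site memo, answered from the medical history already taken at Visit 1. The only downside is the possible loss of a very small number of repeaters, probably none. No sample-size, power or significance-level figure changes.

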**Comparison of High vs. Standard Dose Flu Vaccine in Pediatric Stem Cell Transplant Recipients**

**DMID Protocol Number 16-0117**

**Protocol Version 8.0**

**Date: 9/12/2019**

**Criteria for temporarily delaying vaccine administration:** The following conditions are temporary or self-limiting, and a subject may be included in the study once the condition has resolved, provided that the subject is otherwise eligible: 1). Fever  $\geq 100.4^{\circ}\text{F}/38.0^{\circ}\text{C}$  (oral measurement), or an acute illness within 48 hours of enrollment 2). Receipt of any live vaccines within four weeks or any inactivated vaccines within two weeks prior to potential study vaccination.

Note: if patients were eligible for vaccine 1, they will be eligible to receive vaccine 2 regardless of any changes on their GVHD status, unless it is deemed not medically safe to receive influenza vaccine.

Note: Previous Screen failures who were not vaccinated can be enrolled and will be assigned the same study ID number.

Comparison of High vs. Standard Dose Flu Vaccine in Pediatric Stem Cell Transplant Recipients

DMID Protocol Number 16-0117

Protocol Version 8.0

Date: 9/12/2019

An overview of the study schedule and procedures are described in **Table 3**.

Table 3.	Screening period	Visit 1	Phone / email	Optional Visit	Visit 2	Phone/Email	Optional Visit	Visit 3	Influenza Season	Visit 4 ^	June 30th
Days		0	1-3 and 8-10* days	5-10 days after visit 1	28-42 days	1-3 and 8-10* days after visit 2	5-10 days after visit 2	28-42 days after visit 2		180 ±42 days after visit 2	Day 0 until June 30th
Consent	X	X									
Inclusion/exclusion		X			X						
Physical examination#, oral temperature		X			X						
Peripheral venipuncture or via central line		X		X	X		X	X		X	
HAI, NAI, and microneutralization assay		X**			X**			X**		X	
B/T cell responses		X		X	X		X	X		X	
CBC d/p#		X			X			X		X	
Quantitative CD4, and CD8, CD19#		X			X			X		X	
Quantitative serum IgG, IgM#		X			X			X		X	
Study vaccine administration (HD-TIV or standard dose)		X			X						
Memory aid review			X			X					
Adverse event assessment		X	X	X	X	X	X				
Concomitant medication collection		X	X	X	X	X	X	X			
Immunizations reviewed		X			X			X		X	
Telephone and/or Electronic communication			X			X			Weekly		
Pregnancy Test (if applicable)		X			X						
Collection of Nasal Swab for PCR testing for Influenza***		X^			X^			X^	If symptomatic	X^	X
Proven clinical influenza illness #review		X	X	X	X	X	X	X	X	X	X

\*8-10 day telephone and/or electronic communication are not required if the subject is seen at the optional visit within this window period;

**Comparison of High vs. Standard Dose Flu Vaccine in Pediatric Stem Cell Transplant Recipients****DMID Protocol Number 16-0117****Protocol Version 8.0**

Date: 9/12/2019

# If these tests/procedures are performed as standard of care prior to enrollment, but on same calendar day of vaccination, they will not need to be repeated and these data can be collected as part of study information.

\*\*a second blood draw will be obtained post-IVIG/SCIG if IVIG/SCIG is administered at this visit.

^a swab will be collected during influenza season.

\*\*\* Nasal swabs will be collected from symptomatic patients throughout the study period.

## Proven clinical influenza illness is any breakthrough influenza illness confirmed by laboratory testing (i.e. Rapid antigen assay, PCR, virus culture, ,etc.

^^ Optional for repeaters in the 2019-20 season

**5. Treatment Groups:** There will be two groups – HD-TIV versus standard dose QIV. The children will be randomized in a 1:1 HD-TIV (100 subjects) versus standard dose QIV (100 subjects) for current enrollment season.

Treatment Group	Target # (all study years)
Group 1 0.5 mL HD-TIV	100
Group 2 0.5 mL standard dose QIV	100

**a. Randomization:** Subjects will be randomized 1:1 to either HD-TIV or standard dose QIV. Randomization will be frequency-matched within each site to ensure balance between the groups and will be implemented using the Randomization Module within Vanderbilt's REDCap database. The investigational pharmacy at each of the 9 institutions will distribute the assigned study vaccine. Because we are evaluating the immunogenicity of early timing of influenza vaccine post-transplant, we will limit enrollment to 60 (30%) subjects to  $\geq 12$  months post-transplant.

